## **1. Background**

Stroke is the leading cause of death in some countries and the leading cause of disability in the world (Roger 2012; Adamson 2004; *The Internet Stroke Center* 2016), significantly contributing to the increase in public health costs. In Brazil, approximately 50% of the people affected present some degree of disability (Carmo 2015) and are dependent on others due to the injury (Allen 2009; Corrêa 2005).

Patients present less symmetry between lower limbs and difficulty in weight bearing on the affected side in standing position, with consequente change in the motor function, balance and gait (Trindade 2011).

Actually there are several approaches to rehabilitation and, between then, virtual reality (VR) - technology that promotes human-computer interaction in an created environment (Laver, 2012) – is expanding in the treatment of post-stroke balance disorders, because VR promotes a motivated, challenging, task-specific and repetitive training (Chen 2016, Laver 2012; Yatar 2015; Joo 2010; Saposnik 2011). The commercial equipment Nintendo Wii Fit®, promote anterior, posterior and lateral excursiono f the center os pressure, allowing greater postural control and symmetry, besides, providing cognitive demand of the decision making to perform the motor task effectively (Crosbie, 2007; Broeren, 2008; Joo, 2010; Cameirão, 2011).

Some studies report the possibility of using this system at home, where the training could be carried out autonomously by the patients themselves, without a physiotherapist directing the training (Yatar 2015; Sugarman 2009; Deutsch 2009). However, as suggested by Yatar in 2015, this issue still controversial - different authors cite the possibility of training without supervision of the physiotherapist but discuss the lack of evidence, questioning the need of the presence of the physiotherapist intervening in the treatment, in order to guarantee patient motivation and safety (Joo 2010, Borghese 2013, Laufer 2014). Thus, there is a need to clarify the role of physical therapist assistance during balance training through VR in comparison to that performed without intervention.

## **2. Purpose**

The aim of this study is to compare the effects of a balance training program in a virtual environment (using a gaming system with balance board device) with and without

verbal/manual physiotherapeutic intervention, on the motor function, balance and gait in chronic stroke patients.

### **3. Methods**

It will be a prospective, single blinded, randomized clinical trial, performed at Center of Research of the Department of Speech Therapy, Physical Therapy and Occupational Therapy of São Paulo University.

Forty chronic stroke patients will be randomly in control and experimental group, 20 each one. Both groups conduct 14 training sessions, twice a week, for seven weeks. Each session will consist a 30 minute-global-exercise series including stretching, muscle strength and axial mobility exercises. After this, both groups will perform 30 more minutes of balance training using eight Wii Fit® games which stimulate motor and cognitive functions.

Patients will be assessed at the beginning, in the end and 60 days after the end of the treatment (follow-up).

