#### **3.1 Participant allocation**

Patients will be randomized in two groups: Experimental Group or Control Group. Each participant must sign the Consent Form.

Forty patients will be selected according to the following criteria:

Inclusion Criteria:

- hemiparetic status resulting from a single stroke at least 6 months earlier;
- the ability to walk 10 m independently with or without an assistive device;
- a Montreal Cognitive Assessment (MoCA) score of  $\geq 20$ ;
- the absence of a musculoskeletal condition that could potentially affect the ability to stand or walk safely;
- absence of serious visual impairment or a hearing disorder;
- muscle strength  $\geq 3$  in lower limbs;
- ability to understand and follow simple instructions.

Exclusion Criteria:

- severe dementia or aphasia;
- hemispatial neglect, ataxia or any other cerebellar symptom;
- inability to stand without minimal assist;
- uncontrollable medical complications;
- participation in other studies or rehabilitation programs.

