### **3.2 Procedures**

#### **3.2.1 Assessments**

Both groups will be assessed before treatment, after treatment and after 60 days of the end of the treatment (follow-up).

Primary outcomes:

- The lower limb subscale of the Fugl-Meyer Assessment (FMA-LE): FMA-LE is a subscale measuring lower limb motor recovery. It examines movement and coordination of the hip, knee, and ankle in the supine, sitting, and standing positions. Each item is scored on a 3-point scale (0, cannot perform; 1, partially performs; 2, performs fully). The score range is 0 to 34, with higher scores indicating better lower limb motor performance (Fugl-Meyer, 1975; Maki, 2006).
- Balance Evaluation Systems Test (BESTest): Balance Evaluation Systems Test (BESTest) measures balance. It includes 36 items that evaluate performance of
  - 6 balance systems: biomechanical constraints, stability limits/verticality, anticipatory postural adjustments, postural responses, sensory orientation, and stability in gait (Horak, 2009).
  - 6-minute walk test: The 6MWT is a practical simple test. This test measures the distance that a patient can quickly walk on a flat, hard surface in a period of 6 minutes (the 6MWD). The 6MWT has been used as a measure of functional status of patients (Britto, 2006).

Secondary outcomes:

- Limits of Stability: The Limits of Stability subtest quantifies the maximum distance a person can intentionally displace their center of pressure (COP) from start position of midline COP centered over the base of support to eight targets.

Location and movement of the COP was indicated by a cursor display projected on a screen in front of the subject. As targets were highlighted, the subject was to move the COP cursor quickly and accurately as possible towards a target located on the Limits of Stability perimeter and hold position as close to the target as possible. The parameters include COP movement velocity and directional control (% to target).

- Rhythmic Weight Shift: The Rhythmic Weight Shift quantifies the subject's active weight shift ability by moving the COP cursor to match velocity and direction of a moving visual target in the medial- lateral (ML) and anterior-posterior (AP) directions at three different velocities.

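### With 20 per arm, no balancing factor described and no baseline covariate, a chance baseline gap above 0.5 SD on at least one primary outcome is expected in about 18–30% of trials, and the planned ANOVA removes only part of it

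*Combined protocol and SAP*

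**What the plan says.** On allocation, section 3 (Methods) states "Forty chronic stroke patients will be randomly in control and experimental group, 20 each one", and section 3.1 (Participant allocation) adds "Patients will be randomized in two groups: Experimental Group or Control Group". No stratification, blocking or minimisation is described in either place.

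The entry criteria in 3.1 set floors on function. They require "the ability to walk 10 m independently with or without an assistive device" and "hemiparetic status resulting from a single stroke at least 6 months earlier", and they exclude "inability to stand without minimal assist". No upper limit on walking, balance or motor score is given.

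Section 3.2.1 names three primary outcomes: FMA-LE ("The score range is 0 to 34, with higher scores indicating better lower limb motor performance"), BESTest and the 6-minute walk test. All are measured before treatment, after treatment and 60 days after treatment ends. No standard deviations or correlations are given.

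Section 3.3 compares demographic and clinical characteristics between groups by unpaired t-test. It then analyses each outcome with a group by evaluation (2x3) repeated-measures ANOVA. The pre-treatment value enters as one of the three repeated levels, not as a covariate.

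**The concern.** In a trial of 40, chance can leave the two groups visibly different in baseline severity. Two tools limit the consequences: balancing a severity measure at allocation, and adjusting for baseline in the analysis. The plan describes neither. The baseline t-test can flag a gap but corrects nothing.

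What is at stake is the reading of the single realised trial. If one group starts worse on, say, BESTest, part of its later gain relative to the other group is expected from regression to the mean, whatever the training does. With three primary outcomes there are three chances for this to happen. The plan also forgoes some precision, which a trial of this size can ill afford.

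**Working it through.** **Inputs from the documents.** 20 patients per arm; three primary outcomes; baseline measured on all three; no balancing factor described; no covariate. The documents state no imbalance probability, so there is no figure of theirs to reproduce.

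**Assumptions, not in the documents.** A gap counts as sizeable above 0.5 SD. The three outcomes share a common correlation r. The pre-post correlation is ρ. Scores are roughly normal. The treatment comparison is read from the group-by-time term, which 3.3 does not say explicitly.

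**Step 1: one outcome.** The standard error of the difference in baseline means is √(2/20) = 0.316 SD. P(|gap| > 0.5 SD) = 2(1 − Φ(0.5/0.316)) = 11.4%.

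**Step 2: at least one of three.** If independent, 1 − (1 − 0.114)³ = 30.4%. With a common correlation, from 1,000,000 simulated draws at each value:

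| r | 0 | 0.3 | 0.5 | 0.6 | 0.7 | 0.8 | 0.9 |
|---|---|---|---|---|---|---|---|
| P(any gap > 0.5 SD) | 30% | 29% | 27% | 25% | 23% | 21% | 18% |

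The result depends strongly on the threshold. For r from 0 to 0.9 it is 50% to 31% at 0.4 SD, and 16% to 10% at 0.6 SD.

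**Step 3: what the planned analysis leaves.** With no treatment effect and a 0.5 SD baseline gap, the expected post-treatment gap is 0.5ρ. The expected difference in change is therefore (1 − ρ) × 0.5 in absolute size: 0.25 SD at ρ = 0.5, 0.15 SD at 0.7 and 0.10 SD at 0.8. At ρ = 0.7 the standard error of the difference in change is √(2 × 0.3) × 0.316 = 0.245 SD, so the leftover is 0.15/0.245 = 0.6 standard errors.

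**Step 4: gain from baseline adjustment.** For one post-treatment comparison, the variance relative to change scores is (1 − ρ²)/(2(1 − ρ)). At ρ = 0.7 this is 0.51/0.60 = 0.85. Estimating the slope from 40 patients multiplies it by about 1 + 1/36, giving 0.874, or about 13% lower variance. The same formula gives about 23% at ρ = 0.5 and 7–8% at ρ = 0.8.

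**Step 5: gain from stratifying on BESTest.** A median split leaves a share 1 − 2/π = 0.363 of the variance of the gap in BESTest itself. Its standard error falls to 0.316 × √0.363 = 0.191 SD, and P(gap > 0.5 SD) falls from 11.4% to 0.9%. The other two outcomes benefit only through their correlation with BESTest. Simulating two strata with randomly varying blocks of 2 and 4:

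| r | 0.3 | 0.5 | 0.7 |
|---|---|---|---|
| Unstratified, any of three | 29% | 27% | 23% |
| Stratified, any of three | 20% | 16% | 11% |

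**The case against.** The case for leaving the plan alone is substantial.

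- **Validity.** Unstratified randomisation is a legitimate choice. Chance imbalance does not bias the comparison on average, and the standard error of the test already allows for it. This stands. A reader might infer that the trial's result would be biased; the documents do not support that.
- **The planned analysis already helps.** Because baseline is one of the repeated levels, the group-by-time term compares changes and removes the raw level difference. At ρ = 0.7 it takes out 70% of the gap (0.35 of 0.5 SD). This also stands: the analysis cannot be said to ignore baseline, only to over-correct for it in a way that a covariate would avoid.
- **The entry criteria do not produce the figure.** It is tempting to say that the absence of an upper limit on function causes the imbalance. In SD units the probability depends on the sample size, the threshold and the correlation. A wider range only makes the same gap larger in points or metres, and a severity stratifier more useful.
- **Foreseeable allocation.** A reader might infer from the fixed 20/20 total that late assignments can be predicted. How many would be depends on how the list is made, which the documents do not say. Nor do they say that the treating physiotherapist enrols patients.
- **Redundancy.** Once each outcome is adjusted for its own baseline, stratifying adds little precision. This is right, and it sets the order of the two changes below.

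What survives is that neither tool is described, that part of any gap carries into the comparison of changes, and that the remedy uses measurements already planned.

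**Conclusion.** The point holds as a modest, inexpensive improvement: one to consider. A baseline gap above 0.5 SD on at least one primary outcome is expected in about 18–30% of trials of this design, and in about 25% at r = 0.6. After such a gap, the expected difference in change with no treatment effect is 0.10–0.25 SD for ρ from 0.8 to 0.5.

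The probability rests on an assumed threshold and assumed between-outcome correlations, and the leftover on an assumed pre-post correlation; none of these is in the documents. At thresholds of 0.4 to 0.6 SD the probability runs from 50% down to 10%, so it should always be quoted with its assumptions. The documents support saying that no balancing factor is described; they do not show that none will be used.

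**What to change.** **1. Section 3.3 (the larger gain).** Analyse the post-treatment and follow-up values of each outcome in a repeated-measures model with group, visit and group-by-visit, that outcome's own baseline as a continuous covariate, and the stratification factor if the second change is made. Adjusting only for a dichotomised BESTest would not deal directly with regression to the mean in FMA-LE or the 6-minute walk.

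**2. Sections 3 and 3.1.** Suggested text: *After the baseline assessment, patients are allocated 1:1 by a concealed computer-generated list, stratified by baseline BESTest (below, or at or above, a cut fixed before the first patient), with randomly varying block sizes. The arm is revealed only once the baseline data have been entered.*

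Minimisation with an 80% random element would be a weaker choice here. In simulation (assumed 50% walking-aid use, median BESTest cut), someone who knew earlier assignments and both factors guessed about 72% of allocations correctly, against 59% for a shuffled list of 20 and 20.

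**Cost.** No extra visit or measurement is needed. Final totals may be 19/21 instead of exactly 20/20, baseline scoring must be finished before allocation, blocks carry some predictability, and one or two degrees of freedom are used. The documents give no BESTest distribution, so the cut may fall away from the median, and the gain in balance would then be smaller than shown.

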#### **3.1 Participant allocation**

Patients will be randomized in two groups: Experimental Group or Control Group. Each participant must sign the Consent Form.

Forty patients will be selected according to the following criteria:

Inclusion Criteria:

- hemiparetic status resulting from a single stroke at least 6 months earlier;
- the ability to walk 10 m independently with or without an assistive device;
- a Montreal Cognitive Assessment (MoCA) score of  $\geq 20$ ;
- the absence of a musculoskeletal condition that could potentially affect the ability to stand or walk safely;
- absence of serious visual impairment or a hearing disorder;
- muscle strength  $\geq 3$  in lower limbs;
- ability to understand and follow simple instructions.

Exclusion Criteria:

- severe dementia or aphasia;
- hemispatial neglect, ataxia or any other cerebellar symptom;
- inability to stand without minimal assist;
- uncontrollable medical complications;
- participation in other studies or rehabilitation programs.

### **3.2 Procedures**

#### **3.2.1 Assessments**

Both groups will be assessed before treatment, after treatment and after 60 days of the end of the treatment (follow-up).

Primary outcomes:

- The lower limb subscale of the Fugl-Meyer Assessment (FMA-LE): FMA-LE is a subscale measuring lower limb motor recovery. It examines movement and coordination of the hip, knee, and ankle in the supine, sitting, and standing positions. Each item is scored on a 3-point scale (0, cannot perform; 1, partially performs; 2, performs fully). The score range is 0 to 34, with higher scores indicating better lower limb motor performance (Fugl-Meyer, 1975; Maki, 2006).
- Balance Evaluation Systems Test (BESTest): Balance Evaluation Systems Test (BESTest) measures balance. It includes 36 items that evaluate performance of
  - 6 balance systems: biomechanical constraints, stability limits/verticality, anticipatory postural adjustments, postural responses, sensory orientation, and stability in gait (Horak, 2009).
  - 6-minute walk test: The 6MWT is a practical simple test. This test measures the distance that a patient can quickly walk on a flat, hard surface in a period of 6 minutes (the 6MWD). The 6MWT has been used as a measure of functional status of patients (Britto, 2006).

Secondary outcomes:

- Limits of Stability: The Limits of Stability subtest quantifies the maximum distance a person can intentionally displace their center of pressure (COP) from start position of midline COP centered over the base of support to eight targets.

Location and movement of the COP was indicated by a cursor display projected on a screen in front of the subject. As targets were highlighted, the subject was to move the COP cursor quickly and accurately as possible towards a target located on the Limits of Stability perimeter and hold position as close to the target as possible. The parameters include COP movement velocity and directional control (% to target).

- Rhythmic Weight Shift: The Rhythmic Weight Shift quantifies the subject's active weight shift ability by moving the COP cursor to match velocity and direction of a moving visual target in the medial- lateral (ML) and anterior-posterior (AP) directions at three different velocities.

- Stroke specific quality of life scale: Stroke Specific Quality of Life Scale is a self-report assessment that includes 12 stroke specific subscales with 49 items. The Stroke Specific Quality of Life Scale attempts to capture the domains of stroke specific QOL that are insufficiently assessed with generic QOL measures. The 12 subscales, which are unidimensional, are Energy, Family Role, Language, Mobility, Mood, Personality, Self-Care, Social Roles, Thinking, Upper Extremity Function, Vision, and Work-Productivity. Participants responded to each item on a 5-point scale. Domain scores are the averages of the item scores, and the total score is the average of the domain scores. All summary scores therefore range from 1 to 5. Higher scores indicate better function (Williams, 1999; Lima, 2006; Lima, 2008).

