### **3.2.2 Training**

Both groups will participate of 14 individual treatment sessions, with physiotherapist supervision, twice a week, for seven weeks. Each treatment session will be composed of 30 minutes of regular physical therapy (equal to both groups), based on stretching, strength and mobility exercises, followed by 30 minutes of balance training using a gaming system with balance board device (eight games of Nintendo Wii Fit®, for games per session).

Differences between groups are based on the type of physiotherapist's role in the training:

Virtual Reality Training Without Physiotherapeutic Intervention (Experimental Group) will perform a balance training program in a virtual environment (using a gaming system with balance board device - eight games of Nintendo Wii Fit®, for 14 sessions)

without verbal/manual physiotherapeutic intervention. Initially, physiotherapist will provide instructions about the rules and strategies of how to play the game and control the avatar. Then the patient will be invited to start the game, and in the two attempts of the training no manual or verbal assistance will be provided by the physiotherapist. Physiotherapist participation during training will be restricted to ensuring patient safety, providing motivational verbal stimuli, and replicating the feedback provided by the game at the end of each attempt.

Virtual Reality Training With Physiotherapeutic Intervention (Control Group) will perform a balance training program in a virtual environment (using a gaming system with balance board device - eight games of Nintendo Wii Fit®, for 14 sessions) with verbal and manual physiotherapeutic intervention. Initially, physiotherapist will provide instructions about the rules and strategies on how to play the game and control the avatar. Then the patient will be invited to start the game, and in the first attempt of the training physiotherapist will provide manual and verbal assistance, providing corrections on movement speed, direction, acceleration, amplitude, rhythm and coordination, necessary to achieve game goals (avoiding compensatory movements). In the second attempt, no manual or verbal assistance will be provided by the physiotherapist (only ensuring patient safety and providing motivational verbal stimuli, and replicating the feedback provided by the game), allowing the patient to organize his or her performance.

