### **3.3 Statistical Analysis**

Demographic data and clinical characteristics of the control and experimental groups will be compared using the unpaired T-test.

Results of the primary and secondary measures will be analyzed after normality test (Kolmogorov-Smirnov test), with repeated measures of variance (ANOVA), one for each dependent variable, using as a factor group (GC and GE) and the three evaluations (before treatment, after treatment and follow up), the last measure being repeated (2x3 RM-ANOVA).

The Tukey Post Hoc Test will be performed to verify any differences between effects with significance.

Significance level adopted: 5%.

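### Post-baseline assessments are timed from the end of treatment, with no rule for patients who stop early, so early stoppers may be measured weeks ahead of the others or lost from the analysis

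*Combined protocol and SAP*

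**What the plan says.** Two places set the schedule. Section 3.2.1 has "Both groups will be assessed before treatment, after treatment and after 60 days of the end of the treatment (follow-up", and section 3 has "Patients will be assessed at the beginning, in the end and 60 days after the end of the treatment (follow-up". Neither counts time from entry or gives a visit window.

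The planned course is the same in both arms. Section 3 states "Both groups conduct 14 training sessions, twice a week, for seven weeks", and section 3.2.2 repeats it with supervision added: "Both groups will participate of 14 individual treatment sessions, with physiotherapist supervision, twice a week, for seven weeks".

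Section 3.3 fits one ANOVA per outcome, with group and "the three evaluations (before treatment, after treatment and follow up), the last measure being repeated (2x3 RM-ANOVA" as factors.

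The plan does not say what counts as the end for a patient who stops, whether missed sessions are made up, which patients are analysed, or how missing values are handled.

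Two further places bear on whether stopping could differ by arm. Section 1 describes authors as "questioning the need of the presence of the physiotherapist intervening in the treatment, in order to guarantee patient motivation and safety". Section 3.2.2 has the physiotherapist keep patients safe and encourage them in the experimental arm, and uses the same terms for the control arm's second attempt. The arms differ in the hands-on and spoken correction that only the control arm receives, during the first attempt.

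**The concern.** The course is defined by a number of sessions and by a number of weeks. The two agree for a patient who attends everything, and the schedule then works. For a patient who stops early, the visit date, and whether there is a visit at all, depends on something that happens after randomisation.

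Two consequences follow under a literal reading:

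- **Measured early.** The first post-baseline score is taken when training stops and enters the ANOVA at the same level as scores taken at week 7.
- **Not measured.** The patient never reaches a post-treatment visit. A classical repeated-measures ANOVA, as usually run, needs all three values, so the whole patient is lost, baseline included. This is a property of the method; the plan does not state it.

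No later analysis can restore a visit that was not made, so the visit schedule has to settle the matter. The sample is small ("Forty chronic stroke patients will be randomly in control and experimental group, 20 each one"), and each patient is 1/20 = 5% of an arm. At stake are precision and a clear time point in any case, and the comparison between arms if stopping is unequal.

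**Working it through.** **Inputs from the documents:** 14 sessions, 2 per week, 7 weeks (sections 3 and 3.2.2); follow-up 60 days later (sections 3 and 3.2.1); 20 patients per arm (section 3); 5% significance level (section 3.3). **Assumed, because the documents give none:** stopping proportions, how much worse stoppers do, and a two-sided test.

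**1. The plan's own schedule.** 14 / 2 = 7 weeks, or day 49. 60 / 7 = 8.6 weeks, so follow-up falls at 7 + 8.6 = 15.6 weeks, or day 109. The stated course reproduces exactly.

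**2. A patient who stops after session 4.** 4 / 2 = week 2 (day 14); follow-up at 2 + 8.6 = week 10.6 (day 74). Both visits are 49 − 14 = 35 days early.

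**3. A patient who runs late but completes.** At an assumed 1.5 sessions per week, 14 / 1.5 = week 9.3, and follow-up is at 9.3 + 8.6 = week 17.9.

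**4. Shift in the arm difference if stoppers are lost.** Let p be the proportion stopping in an arm, and d the mean change from baseline in completers minus that in stoppers, in SD units and equal in both arms. The mean over all patients is (1 − p) × completers + p × stoppers, so the completers' mean exceeds it by p × d. The arm difference shifts by (difference in p) × d, in favour of the arm with more stoppers when stoppers do worse.

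| Assumed stopping | d = 0.5 SD | d = 1.0 SD |
|---|---|---|
| 10% vs 10% | 0 | 0 |
| 20% vs 10% | 0.10 × 0.5 = 0.05 SD | 0.10 × 1.0 = 0.10 SD |
| 20% vs 5% | 0.15 × 0.5 = 0.075 SD | 0.15 × 1.0 = 0.15 SD |

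Here d concerns change, not level. In a 2x3 ANOVA the treatment effect over time is the group-by-time interaction. If stoppers were worse by the same amount at every visit, d would be 0, and losing them would not bias the interaction.

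**5. Timing imbalance if stoppers are measured early.** With 20% versus 10% stopping after session 4, the mean visit time differs between arms by 0.10 × 35 = 3.5 days. What that does to the scores depends on how they move between weeks 2 and 7, which the documents do not say.

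**6. Scale.** For a single two-arm comparison with 20 per arm (normal approximation), 80% power corresponds to (1.960 + 0.842) × √(2/20) = 0.89 SD. If 20% are lost in each arm (16 per arm), power for that difference falls to about 71%.

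**The case against.** **The Background does not show that stopping will be unequal.** A reader might infer from section 1 that the experimental arm will lose more patients because motivation and safety suffer without intervention. The documents do not support that. Section 1 follows a discussion of unsupervised home training, which neither arm receives, and calls the matter controversial and short of evidence. Section 3.2.2 provides supervision, safety cover and encouragement in both arms. This objection stands. It leaves unequal stopping possible, since correction is given in one arm only, but not established.

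**The text does not prescribe week-2 visits or exclusion.** The planned seven weeks could be read as fixing the end of treatment for everyone, and section 3.2.1 does not restrict assessment to completers. That is fair: early measurement and loss are readings of a silent text. But nothing in the text chooses among the readings, and the choice could differ from patient to patient.

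**Timing from the end of training is a coherent choice.** A reader might conclude that the anchor is an error and that every patient should be assessed at calendar week 7. The documents do not support that either. Section 2 asks about the effects of a training programme, and a follow-up counted from its end suits that aim. Strict week-7 timing would also have a cost. At 1.5 sessions per week a late runner would be assessed after 7 × 1.5 = 10.5 of 14 sessions. Training would end at day 65.3 (9.33 × 7), so a day-109 follow-up would come about 44 days after it, not 60. This objection stands for patients who complete late, and the fix leaves them alone.

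**The possible shift is small.** 0.05 to 0.15 SD is well below the 0.89 SD that 20 per arm could detect with 80% power. That is true. It limits the importance of the point, but the remedy needs no new tests or scheduled visits.

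**Conclusion.** The point holds for patients who stop early or do not complete the course. Both post-baseline assessments hang on an end of treatment that is undefined for these patients, and the analysis treats the results as common time points. Read literally, a patient who stops after session 4 is measured 5 weeks early at both visits, or is lost.

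Bias between arms requires both unequal stopping and a different change from baseline in stoppers. Under the assumed rates it is 0.05 to 0.15 SD; if either condition fails, losing stoppers causes none. With similar stopping in both arms, what remains is a blurred time point and lost precision. Every stopping rate and SD gap here is an assumption. The change should be made, but the gap does not invalidate the design.

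**What to change.** **Sections 3 and 3.2.1.** State that every randomised patient is invited to both post-baseline assessments, whatever the number of sessions attended. For a patient who stops early, hold them at the end of the planned seven weeks, counted from the first session, and 60 days after that date. Patients who complete the course keep the current timing. Record actual dates for everyone.

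**Section 3.3.** Analyse all randomised patients in their assigned arm using all available assessments. Since a classical repeated-measures ANOVA drops incomplete patients, this needs a method that accepts them, for example a mixed model with the same group and time factors. Report sessions attended and reasons for stopping by arm.

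**Cost.** Protocol wording and a modest change of analysis method; the scheduled visits and tests stay the same. Patients who stop must be invited back, and some may decline. The decision to stop training is unchanged.
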